2.3.3 SECONDARY OUTCOME – RESPONSE TIME

RATIONALE. Participants make a button press on a keyboard to indicate if the probed items are matched or non-matched to the items held in memory. The investigators will calculate the response time for each condition. Theta oscillations are known to be generated in frontal cortex when cued to the contralateral visual field. Alpha oscillations are known to be generated in parietal cortex when cued to the ipsilateral visual field.

ALTERNATIVE HYPOTHESIS. When the frequency of TMS to either frontal or parietal cortex is compatible with the endogenous activity, response time should decrease relative to TMS that is incompatible. Therefore, we will report the TMS compatibility effect as the average of "theta minus alpha TMS to frontal cortex for retro-cue right" and "alpha minus theta TMS to parietal cortex for retro-cue left". We will report the mean and standard deviation of the TMS compatibility effect across participants. This effect will be investigated using repeated-measures two-way ANOVA, and an interaction between TMS site and TMS frequency is hypothesized.

NULL HYPOTHESIS. There is no systematic effect of frequency specific TMS on response time.

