11.1 STATISTICAL ANALYSIS STRATEGIES

To control for non-specific effects of rhythmic TMS, we will use an active control: arrhythmic TMS (randomized inter-pulse-interval) that is matched to the target stimulation in number of pulses and temporal duration. All analyses will be run on the difference from condition-matched arrhythmic TMS. The key analysis is a two-way repeated-measures ANOVA with factors TMS frequency (theta vs alpha) and location (inferior-IPS vs anterior-MFG). Post-hoc t-tests will be run on a significant main effect of TMS frequency, TMS site, or interaction. We will use Tukey's adjusted significance for post-hoc testing to correct for multiple comparisons.

Primary outcome: working memory capacity. Two-way repeated-measures ANOVA run on the difference from arrhythmic TMS with factors (TMS site and TMS frequency). The direction of the retro-cue is held consistent for each site: for TMS to frontal cortex (anterior-MFG) the retro-cue to the right is used, and for TMS to parietal cortex (inferior-IPS) the retro-cue to the left is used. We hypothesize that theta frequency rhythmic TMS will improve behavioral performance when applied to anterior-MFG; i.e. a main effect of TMS frequency and/or an interaction between TMS frequency and cue. We hypothesize that alpha frequency rhythmic TMS will improve behavioral performance for retro-cue trials when applied to inferior-IPS; i.e. an interaction between TMS frequency and cue.

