Primary outcome: Spectral power. We collected EEG recording during the delivery of rhythmic TMS. We hypothesize, based on previous studies with identical rhythmic TMS trains, that rhythmic TMS will entrain neural oscillations in the targeted frequency. We will quantify entrainment from rhythmic TMS by analyzing the spectral decomposition of the EEG signal during TMS and immediately after TMS. We will run a six-cycle Morlet wavelet convolution with the EEG signal to estimate spectral density (microvolts per hertz). We hypothesize that the amplitude of theta activity will be increased following theta rhythmic TMS relative to theta activity following arrhythmic TMS. Similarly, alpha amplitude will be increased following alpha rhythmic TMS relative to alpha amplitude following arrhythmic TMS. The direction of the retro-cue is held consistent for each site: for TMS to frontal cortex (anterior-MFG) the retro-cue to the right is used, and for TMS to parietal cortex (inferior-IPS) the retro-cue to the left is used. We hypothesize an interaction between TMS frequency and cue.

Primary outcome: response time. Two-way repeated-measures ANOVA run on the difference from arrhythmic TMS with factors (TMS site and TMS frequency). The direction of the retro-cue is held consistent for each site: for TMS to frontal cortex (anterior-MFG) the retro-cue to the right is used, and for TMS to parietal cortex (inferior-IPS) the retro-cue to the left is used. We hypothesize that theta frequency rhythmic TMS will improve behavioral performance (decreased response time) when applied to anterior-MFG; i.e. a main effect of TMS frequency and/or an interaction between TMS frequency and cue. We hypothesize that alpha frequency rhythmic TMS will improve behavioral performance (decreased response time) for retro-cue trials when applied to inferior-IPS; i.e. an

interaction between TMS frequency and cue.

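### Response time is secondary in 2.3.3 but primary in 11.1, and for the behavioural outcomes 11.1 adds a TMS frequency main effect to the site-by-frequency interaction that 2.3 hypothesises and 11.2 powers

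*Combined protocol and SAP*

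**What the plan says.** **Status of response time.** The heading of section 2.3.3 reads "SECONDARY OUTCOME – RESPONSE TIME". Section 11.1 reads "Primary outcome: response time". Both are current text.

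**Effect of interest.** Sections 2.3.1 to 2.3.3 each report a single quantity, the TMS compatibility effect. It is the average of theta minus alpha at the frontal site (right cue) and alpha minus theta at the parietal site (left cue). Each section hypothesises a TMS site by TMS frequency interaction and no other ANOVA term. Section 11.2 takes its 0.532 and N = 48 from that interaction for working memory capacity.

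**Analysis.** Section 11.1 sets a two-way repeated-measures ANOVA (frequency, location) on differences from arrhythmic TMS. For both behavioural outcomes it then expresses the frontal theta hypothesis as "a main effect of TMS frequency and/or an interaction between TMS frequency and cue". It does not mention the compatibility effect. It also says "The direction of the retro-cue is held consistent for each site", so cue is not a separate factor.

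**Spectral power.** Section 11.1 hypothesises a frequency-by-cue interaction. It also expects that "amplitude of theta activity will be increased following theta rhythmic TMS relative to theta activity following arrhythmic TMS" and that "alpha amplitude will be increased following alpha rhythmic TMS relative to alpha amplitude following arrhythmic TMS". Entrainment is quantified by "analyzing the spectral decomposition of the EEG signal during TMS and immediately after TMS".

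**Multiplicity.** The only rule is Tukey's "adjusted significance for post-hoc testing to correct for multiple comparisons". Neither alpha nor a way of reading the primary outcomes together is given.

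**The concern.** The plan has two primary outcomes or three, depending on the section read. For the behavioural outcomes it also names two ANOVA terms, of which only one is the effect that the study was designed and sized to detect.

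Suppose theta beats alpha by the same amount at both sites. The parietal-alpha half of the hypothesis is then contradicted and the compatibility effect is zero, yet the words of 11.1 leave room to report support for the working memory hypothesis on the frequency main effect. Section 11.2 concludes that the study is adequately powered for its hypotheses. That statement has a definite meaning only once the test that answers each hypothesis is named.

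**Working it through.** **Step 1: reproduce the sample sizes.** Inputs are the three effect sizes in 11.2 and 95% power. Alpha and sidedness are not stated. For a paired t-test, power = P(|T| > t(0.975, n-1)), with T noncentral t on n-1 degrees of freedom and noncentrality d x sqrt(n).

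- d = 0.532: n = 48 (power 95.05%; 94.6% at n = 47)
- d = 0.83: n = 21 (95.1%)
- d = 0.56: n = 44 (95.3%)

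All three match. One-sided 0.05 would give 40, 18 and 36. Two-sided 0.05 is therefore assumed below.

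**Step 2: the contrasts.** Let A = theta minus alpha at the frontal site and B = theta minus alpha at the parietal site.

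- Compatibility effect = (A - B)/2, which is half the site-by-frequency interaction contrast.
- Frequency main effect = (A + B)/2.

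If A = B, the compatibility effect is 0 and the main effect is A. The arrhythmic subtraction does not change this, because within a site (theta - arrhythmic) - (alpha - arrhythmic) = theta - alpha. Only right-cue frontal and left-cue parietal cells are analysed, so frequency by cue is the same contrast as frequency by site. It is a labelling slip and not an extra test.

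**Step 3: one behavioural outcome.** The covariance of A - B and A + B is var(A) - var(B). With equal variances the two tests are effectively independent.

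- False-positive chance, interaction only: 5%.
- False-positive chance, either term: 1 - 0.95^2 = 9.75% (simulated at n = 48: 9.8%).
- Power at d = 0.532, interaction only: 95.05%.
- Power at d = 0.532, either term: 1 - (1 - 0.9505) x 0.95 = 95.3% (simulated: 95.3%).

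**Step 4: across primary outcomes.** All nulls true, each test at two-sided 0.05, any rejection counted. WM = working memory capacity, SP = spectral power, RT = response time, I = interaction, F = frequency main effect. The simulation uses n = 48, equal-variance independent noise across the site-by-train conditions, and a common correlation r between outcomes.

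| Reading | Tests | 1 - 0.95^k | r = 0 | r = 0.5 | r = 0.8 |
|---|---|---|---|---|---|
| 2.3: WM I, SP I | 2 | 9.75% | 9.7% | 9.1% | 7.9% |
| 11.1, RT not primary: WM I and F, SP I | 3 | 14.3% | 14.4% | 13.7% | 12.6% |
| 11.1, RT primary: adds RT I and F | 5 | 22.6% | 22.8% | 20.9% | 17.1% |

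**Step 5: if alpha were split.** At 0.025 per primary and n = 48, power for d = 0.532 is 91.1%.

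**The case against.** **The single deciding test is inferred.** Section 2.3 never says that the interaction alone decides. Its null, that frequency-specific TMS has no systematic effect, is broad enough to be contradicted by a frequency main effect. This stands: the ambiguity is already present in 2.3, and the fix must reach it.

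**Section 11.1 states hypotheses and no success rule.** The main-effect phrase sits in a sentence about theta at the frontal site, and the next sentence predicts the parietal alpha benefit through the interaction only. Section 4 calls the critical comparison one of frequencies within a single site, so the phrase may mean the simple frequency effect at the frontal site. That is a fair reading, but it is still not the interaction. With the same noise model it gives a false-positive chance of roughly 8 to 9% per behavioural outcome instead of about 10%.

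**It is a pilot** with separate behavioural and EEG nulls. Study-wide error control is therefore a choice, and its absence is not in itself a fault.

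Four stronger readings are tempting, and the documents do not support them:

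- *A false-positive risk of up to 95% through the main effect.* At n = 48 with zero compatibility, the main effect is significant in 27%, 53% and 95% of studies if its true size is 0.20, 0.30 or 0.532. That is power for a real effect of assumed size, not an error rate, and no section suggests a main effect that large.
- *Rates of 26-38% from testing two EEG windows.* Section 11.1 says the signal during and just after TMS is analysed. It does not specify a separate test in each, and its two spectral predictions concern activity following stimulation.
- *The two spectral contrasts as further stand-alone primary tests.* Section 11.1 does not say that either decides the outcome.
- *Section 4.1 as a rival primary test.* Its statement that the primary analysis is rhythmic against arrhythmic TMS can be read as describing the difference scores entered into the ANOVA. It needs aligning, but it is not clearly a competing test.

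**Conclusion.** The point holds on two facts in current text: response time has two statuses, and 11.1 sets a frequency main effect beside the interaction that 2.3 hypothesises and 11.2 powers. The main effect is orthogonal to the compatibility effect and adds almost nothing to power for the planned effect, while roughly doubling the false-positive chance for each behavioural outcome. Combined with the promotion of response time, it about doubles the chance of some false-positive primary result.

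These sizes rest on two-sided 0.05 per test, equal variance of the theta-alpha difference at the two sites, outcome correlations between 0 and 0.8, and each result being read on its own. N = 48 is correct for the interaction and is not in question. The label conflict is certain. The consequences depend on how the and/or wording would be applied, which the plan leaves open. The point should be fixed before analysis.

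**What to change.** 1. In 11.1, label response time secondary, as in 2.3.3.
2. In 11.1, state that for each outcome the deciding test is the TMS site by TMS frequency interaction (the compatibility effect of 2.3). Replace cue by site in the interaction terms. Make main effects and the theta- and alpha-versus-arrhythmic contrasts supportive. Name one EEG window for the spectral power test.
3. Align the null statements in 2.3 and the primary-analysis sentence in 4.1 with that test.
4. State alpha and how the two primaries are read. The smallest change is to call them separate questions, each at two-sided 0.05, without study-wide error control. If a study-level confirmatory claim is intended, choose either a fixed sequence (working memory capacity, then spectral power) or 0.025 each.
5. In 11.2, note that the 0.83 and 0.56 calculations power the simple rhythmic-versus-arrhythmic contrasts, and that the spectral power interaction has no calculation of its own.

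**Cost.** Wording only; 48 completers remain. Working memory power stays at 95% with separate questions or the fixed sequence, and falls to 91% at 0.025 each. The fixed sequence allows no confirmatory EEG claim if working memory fails. Treating the primaries separately accepts a chance of about 8-10% of at least one false-positive primary result.

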11.2 SAMPLE SIZE DETERMINATION

Based on a previous study with the current behavioral paradigm and similar TMS manipulation, the effect size of the interaction between TMS site and TMS frequency on WM capacity was 0.532 and used 21 participants. A power analysis of this effect suggests that to reach 95% statistical power we would need to recruit 48 participants. Therefore, we will run our final analysis on 48 participants. Previous studies using a similar methodology of concurrent rhythmic TMS and EEG to look for changes in oscillatory power of the frequency of rhythmic TMS have used 10 participants for alpha frequency TMS (Thut et al., 2011) and 17 participants for theta rhythmic TMS (Albouy et al. 2017). Here, we propose to collect 48 participants. Therefore, our statistical power exceeds that of previous studies published in high-impact journals using a nearly identical methodology. Furthermore, we utilize a repeated-measures inter-mixed design in order to maximize our ability to control for confounding variables and increase statistical power. Based on a previous study by Thut et al., 2011 that found an increase in alpha oscillatory power from alpha rhythmic TMS relative to arrhythmic TMS with an effect size of 0.83 and 10 participants, we would need 21 participants to reach 95% statistical power for this comparison. Based on a previous study by Albouy et al., 2017 that found an increase in theta oscillatory power from theta rhythmic TMS relative to arrhythmic TMS with an effect size of 0.56 and 17 participants, we would need 44 participants to reach 95% statistical power for this comparison. Therefore, we estimate that based on these previously reported effect sizes for the impact of rhythmic TMS on behavior and oscillatory power measured by EEG in similar studies and our proposed sample size of 48 participants, we conclude that the proposed study has sufficient statistical power to answer the posed hypotheses.

11.3 DATA MANAGEMENT

Data will be stored in a password-protected cloud-based data system that does not contain any participant information. Individual records are referred to by dummy identifiers that cannot be traced back to the study participants except with the master code list that is stored separately in a secured location.

Information about study participants will be kept confidential and managed according to the requirements of the Health Insurance Portability and Accountability Act of 1996 (HIPAA). Those regulations require a signed participant authorization informing the participant of the following:

- What protected health information (PHI) will be collected from the participants in this study
- Who will have access to that information and why
- Who will use or disclose that information
- The rights of a research participant to revoke their authorization for use of their PHI.

In the event that a participant revokes authorization to collect or use PHI, the investigator, by regulation, retains the ability to use all information collected prior to the revocation of participant authorization. For participants that

have revoked authorization to collect or use PHI, attempts should be made to obtain permission to collect at least vital status (i.e., that the participant is alive) at the end of their scheduled study period.

The responsibilities designated to each member of the research team are documented on the Delegation of Authority Form. The study coordinator and research assistants will be responsible for the informed consent process, review for eligibility, questionnaire administration, data entry, device administration, EEG administration, and CRF entries. The study coordinator will be responsible for AE/SAE documentation and reporting, while the PI will be responsible for the AE assessment, review of the AE documentation forms, and overview of the research staff.

All data (including AEs, concomitant medications, and expected adverse reactions data) will be entered into a data capture system provided by REDCap. The data system includes password protection and internal quality checks, such as automatic range checks, to identify data that appear inconsistent, incomplete, or inaccurate. Clinical data will be entered directly from the source documents.

All assessments completed by the participant at home will be completed via REDCap as well, ensuring participant security and confidentiality.

All deviations from the protocol will be addressed in study participant source documents. The researcher will complete a Protocol Deviation Log using the participant code as the identifier. This form will collect information such as the date the deviation occurred, details of what the deviation consisted of, any corrective and preventative actions that were taken as a result of the deviation, and the date that the PI and IRB were notified. The PI will review the information and initial once approved. A completed copy of the Protocol Deviation Form will be maintained in the regulatory file, as well as in the participant's source document. Protocol deviations will be sent to the IRB per their guidelines. The site PI/study staff will be responsible for knowing and adhering to their IRB requirements.

According to the University of North Carolina at Chapel Hill's Archives and Record Management Services schedule for General Records Retention and Disposition Schedule 6.10, records will be kept for 5 years after the completion of the study or grant end date, whichever is later.

12 DATA HANDLING AND RECORD KEEPING

The study coordinator and research assistants are responsible for the accuracy, completeness, legibility, and timeliness of the data reported.

12.1 PHI AND HIPAA

Information about study participants will be kept confidential and managed according to the requirements of the Health Insurance Portability and Accountability Act of 1996 (HIPAA). Those regulations require a signed participant authorization informing the participant of the following:

- What protected health information (PHI) will be collected from the participants in this study
- Who will have access to that information and why
- Who will use or disclose that information
- The rights of a research participant to revoke their authorization for use of their PHI.

In the event that a participant revokes authorization to collect or use PHI, the investigator, by regulation, retains the ability to use all information collected prior to the revocation of participant authorization. For participants that have revoked authorization to collect or use PHI, attempts should be made to obtain permission to collect at least vital status (i.e., that the participant is alive) at the end of their scheduled study period.

12.2 CONFIDENTIALITY

12.2.1 ACCESS TO SOURCE DOCUMENTS

The research coordinator, research assistants, and PI will have access to all of the source documents collected over the course of the study. The medical monitor will have access to files upon request, as they will need access to the locked filing cabinets and rooms in which these documents are located.

Data will stay on a password-protected computer. Subsequently, a copy will be processed on a separate, password-protected desktop computer in the [name] Lab ([name]).

12.2.3 OTHER

Please note that there is no significant risk of deductive disclosure in this study. In addition, none of the groupings or subgroupings used in analysis will be small enough to allow individuals to be identified.

12.3 SOURCE DOCUMENTS

Source data is all information, original records of clinical findings, observations, or other activities in a study necessary for the reconstruction and evaluation of the trial. Source data are contained in source documents.

Source data include:

PARTNERS HUMAN RESEARCH COMMITTEE (IRB).

- All IRB correspondences are documented
- The study staff is IRB approved prior to performing any study procedures
- Adverse events and deviations are reported to the IRB per current guidelines and stored appropriately
- All versions of the IRB protocols and informed consent forms are on file

INFORMED CONSENT.

- Ensure that participant identification is not recorded on the ICF (i.e., no participant ID)
- There is documentation that the participant is given a copy of the consent form
- The participant and study representative signed and dated the consent form for him/herself
- The participant initialed and dated all appropriate pages on the informed consent form

- Note to file (Appendix F) made for any informed consent deviations
- Ensure a valid (current version date) copy of the consent form was used

PROTOCOL DEVIATIONS.

- Any and all protocol deviations (exceptions and violations) are documented in the participant folder and reported to the IRB as required

OTHER SOURCE DOCUMENTS.

- Each participant folder will contain a checklist to ensure that all source documents are administered and collected properly. The checklist will be dated by the researcher for each time an assessment is administered
- Review participant folders to ensure the accuracy, completeness, and legibility of the data.
- Any correction made to the source documents is dated, initialed, and explained. The original entry should not be obscured.
- The protocol-specific source documents are on file.
- Source documents are completed in ink.
- Note to files (Appendix F) are made for missing or incomplete data and to explain any discrepancies or additional comments.

12.4 DATA MANAGEMENT RESPONSIBILITIES

The responsibilities designated to each member of the research team are documented on the Delegation of Authority Form. The study coordinator and research assistants will be responsible for the informed consent process, review for eligibility, questionnaire administration, data entry, device administration, EEG administration, and CRF entries. The study coordinator will be responsible for AE/SAE documentation and reporting, while the PI will be responsible for the AE assessment, review of the AE documentation forms, and overview of the research staff.

